7.6.2. Concomitant Medications

Concomitant medications are any medications (excluding study drug and prior anticancer treatments) which started prior to first dose date of study treatment and continued during the on-treatment period as well as those that started during the on-treatment period. Concomitant medications will be summarized based on the Prior and Concomitant Medications eCRF.

Concomitant medications will be coded using the latest version of WHO DRL dictionary available at the time of reporting and will be summarized by ATC classification level 2 and preferred term (level 4).

All concomitant medications will be listed.

Incomplete dates will be handled as described in [Section 7.1.11](#).

7.6.3. Subsequent Anticancer Treatments

Number of participants with any anti-cancer treatment after discontinuation of study treatment will be summarized by type of therapy (systemic treatment, radiotherapy, and surgery). In addition, number of participants who received PD1/L1 therapy after treatment discontinuation will also be summarized. The final list of subsequent PD1/L1 therapy will be provided upon medical review of all subsequent anti-cancer systemic treatment before database lock for analysis.

Summary statistics will be created for the data collected on the Subsequent Cancer Treatment Systemic eCRF page. The best overall response on the subsequent anti-cancer systemic treatments will be summarized by the first and secondary subsequent treatment, and by medication class. The final list of medication class will be provided upon medical review of all subsequent anti-cancer systemic treatment before database lock for analysis.

Anticancer systemic treatments initiated since discontinuation of study treatment will be summarized by ATC class and preferred term.

Incomplete dates will be handled as described in [Section 7.1.11](#).

7.6.4. Adverse Events

Treatment-emergent adverse events (TEAEs) are defined as AEs with onset date during the on-treatment period.

Unless otherwise stated, only TEAEs will be presented in summary tables. However, all AEs will be presented in listings. AEs and SAEs will be coded by PT and SOC using the latest available MedDRA version.

The severity of an AE will be assessed by the investigator using the NCI CTCAE, Version 4.03. For participants with more than 1 AE within a SOC or PT, only the highest grade will be included in by-severity summaries.

The investigator will also assess whether the AE is related to study drugs (i.e., a treatment-related AE). For participants with more than 1 AE within a SOC or PT, the highest level of relationship (related is higher than not related) will be included in the by relationship summaries. AEs will be considered treatment related if they are related to encorafenib and/or binimetinib.

For summaries by SOC and PT, each participant will be counted at most once per SOC and at most once per PT. For summaries by PT, each participant will be counted at most once per PT.

Overall summary of safety table will include numbers and percentages of the following:

- Participants with at least 1 TEAE regardless of causality
- Participants with at least 1 treatment-related TEAE
- Participants with Grade 3 or 4 TEAEs
- Participants with Grade 3 or 4 treatment-related TEAEs
- Participants with Grade 5 TEAEs
- Participants with Grade 5 treatment-related TEAEs
- Participants with at least 1 treatment-emergent SAE
- Participants with at least 1 treatment-related SAE
- Participants who discontinued study drug due to a TEAE regardless of causality
 - TEAE leading to encorafenib discontinuation
 - TEAE leading to binimetinib discontinuation
- Participants with a dose reduction due to a TEAE
 - TEAE requiring encorafenib dose reduction
 - TEAE requiring binimetinib dose reduction
- Participants with a dosing interruption due to a TEAE
 - TEAE requiring encorafenib dosing interruption
 - TEAE requiring binimetinib dosing interruption

All TEAE summaries will be displayed (frequency counts and percentages) alphabetically by system organ class (SOC) and preferred term (PT) by descending frequency within SOC

based on “Total” group, if not otherwise noted. Individual summary tables showing the incidence of participants with the following subsets of TEAEs will be generated:

- TEAEs, regardless of causality, by SOC and PT (All Grades and maximum severity)
- TEAEs, regardless of causality, by PT (All Grades and maximum severity) ordered by decreasing frequency based on “Total” group
- TEAEs, regardless of causality, by PT (Grade 3 and Grade 4) ordered by decreasing frequency based on “Total” group
- Treatment-related TEAEs by PT (All Grades and maximum severity) ordered by decreasing frequency based on “Total” group
- Treatment-related TEAEs, by PT (Grade 3 and Grade 4) ordered by decreasing frequency based on “Total” group
- SAEs, regardless of causality, by PT (All Grades) ordered by decreasing frequency based on “Total” group
- Treatment-related SAEs by PT (All Grades) ordered by decreasing frequency based on “Total” group
- TEAEs, regardless of causality, that led to permanent discontinuation of study drug by PT (All Grades) ordered by decreasing frequency based on “Total” group
 - TEAE that led to permanent encorafenib discontinuation
 - TEAE that led to permanent binimetinib discontinuation
 - TEAE that led to both encorafenib and binimetinib permanent discontinuation
- Treatment-related TEAEs that led to permanent discontinuation of study drug by PT (All Grades) ordered by decreasing frequency based on “Total” group
 - TEAE that led to permanent encorafenib discontinuation
 - TEAE that led to permanent binimetinib discontinuation
 - TEAE that led to both encorafenib and binimetinib permanent discontinuation
- TEAEs that led to reduction in dose of study drug by PT (All Grades) ordered by decreasing frequency based on “Total” group
 - TEAE that led to encorafenib dose reduction
 - TEAE that led to binimetinib dose reduction
 - TEAE that led to both encorafenib and binimetinib dose reduction

- Treatment-related TEAEs that led to reduction in dose of study drug by PT (All Grades) ordered by decreasing frequency based on “Total” group
 - TEAE that led to encorafenib dose reduction
 - TEAE that led to binimetinib dose reduction
 - TEAE that led to both encorafenib and binimetinib dose reduction
- TEAEs that led to interruption of study drug administration by PT (All Grades) ordered by decreasing frequency based on “Total” group
 - TEAE that led to encorafenib dosing interruption
 - TEAE that led to binimetinib dosing interruption
 - TEAE that led to both encorafenib and binimetinib dosing interruption
- Treatment-related TEAEs that led to interruption of study drug administration by PT (All Grades) ordered by decreasing frequency based on “Total” group
 - TEAE that led to encorafenib dosing interruption
 - TEAE that led to binimetinib dosing interruption
 - TEAE that led to both encorafenib and binimetinib dosing interruption.
- The following additional tables will be produced for AESIs. A list of AESIs used for this study will be maintained by the SRL and provided to programming in a different document.
- Summary table of binimetinib and encorafenib treatment-emergent AESIs (any AESI, any treatment-related AESI, SAE, treatment-related SAE, Grade 3 or 4 AESI, treatment-related Grade 3 or 4 AESI, Grade 5 AESI, Grade 5 treatment-related AESI)
- AESIs for binimetinib and encorafenib regardless of causality, by AESI grouping (all grades, Grade 3, Grade 4, Grade 5) ordered by decreasing frequency of all grades
- Treatment-related AESIs for binimetinib and encorafenib, by AESI grouping (all grades, Grade 3, Grade 4, Grade 5) ordered by decreasing frequency of all grades
- Time to First Onset of treatment-emergent AESIs for binimetinib and encorafenib regardless of causality (by AESI grouping)
- Time to First Onset of treatment-related treatment-emergent AESIs for binimetinib and encorafenib (by AESI grouping)
- Serious treatment-emergent AESIs for binimetinib and encorafenib by AESI grouping (all grades) ordered by decreasing frequency of “Total” (all-causality and treatment-related)

Time to AE Onset (in days) is defined as the time from the date of the first dose to the onset date of the AE, regardless of grade. If a participant has multiple episodes of an AE, the date of the first occurrence is used. Time to AE onset (in days) will be calculated as (AE start date – first dose date +1). Time to onset is calculated for the subgroup of participants who had the specific AE.

Descriptive statistics will be presented for time to AE onset (days) for the subgroup of participants with the AESI.

All deaths, deaths within 30 days after last dose of study drug, and deaths > 30 days after last dose of study drug will be summarized. The primary reason for death will be summarized for all deaths and deaths within 30 days after last dose of study drug based on the data collected on the Death eCRF page.

Deaths recorded during the study will be provided in a listing.

All AEs and their attributes will be presented in data listings sorted by participant identifier, AE, and date of onset of the AE.

Incomplete dates will be handled as described in [Section 7.1.11](#).

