7.5.1. Time Period and Frequency for Collecting AE and SAE Information

As of IRB/IEC approval of Amendment 3, the time period for actively eliciting and collecting AEs and SAEs ("active collection period") for each patient begins from the time the patient provides informed consent, which is obtained before the patient's participation in the study (ie, before undergoing any study-related procedure and/or receiving study treatment), through and including a minimum of 30 calendar days, except as indicated below, after the last administration of the study treatment. *Note*: Prior to IRB/IEC approval of Amendment 3 only study procedure related AEs were required to be reported from the time the patient provided informed consent up to the first dose of study treatment.

During the long-term follow up period in this study for survival, only SAEs will be actively elicited and collected after completion of the active collection period described above. The SAEs identified during long-term follow-up will be reported to Pfizer Safety on the CT SAE Report Form only if considered reasonably related to the study treatment.

Follow-up by the investigator continues throughout and after the active collection period and until the AE or SAE or its sequelae resolve or stabilize at a level acceptable to the investigator and Pfizer concurs with that assessment.

For patients who are screen failures, the active collection period ends when screen failure status is determined.

If the patient withdraws from the study and also withdraws consent for the collection of future information, the active collection period ends when consent is withdrawn.

If a patient definitively discontinues or temporarily discontinues study treatment because of an AE or SAE, the AE or SAE must be recorded on the CRF and the SAE reported using the CT SAE Report Form.

Investigators are not obligated to actively seek AEs or SAEs after the patient has concluded study participation. However, if the investigator learns of any SAE, including a death, at any time after a patient has completed the study, and he/she considers the event to be reasonably related to the study treatment, the investigator must promptly report the SAE to Pfizer using the CT SAE Report Form.

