14.1. Definition of AE

| AE Defin | AE Definition | | |
|-----------------|--|--|--|
| • | An AE is any untoward medical occurrence in a patient or clinical study patient, temporally associated with the use of study treatment, whether or not considered related to the study treatment. | | |
| • | NOTE: An AE can therefore be any unfavorable and unintended sign (including an abnormal laboratory finding), symptom, or disease (new or exacerbated) temporally associated with the use of study treatment. | | |

Events Meeting the AE Definition

| ٠ | Any abnormal laboratory test results (hematology, clinical chemistry, or |
|---|---|
| | urinalysis) or other safety assessments (eg, ECG, radiological scans, vital sign |
| | measurements), including those that worsen from baseline, considered |
| | clinically significant in the medical and scientific judgment of the investigator |
| | Any abnormal laboratory test results that meet any of the conditions below |
| | must be recorded as an AE: |
| | |

- Is associated with accompanying symptoms.
- Requires additional diagnostic testing or medical/surgical intervention.
- Leads to a change in study dosing (outside of any protocol-specified dose adjustments) or discontinuation from the study, significant additional concomitant drug treatment, or other therapy.
- Exacerbation of a chronic or intermittent preexisting condition including either an increase in frequency and/or intensity of the condition.
- New conditions detected or diagnosed after study treatment administration even though it may have been present before the start of the study.
- Signs, symptoms, or the clinical sequelae of a suspected drug-drug interaction.
- Signs, symptoms, or the clinical sequelae of a suspected overdose of either study treatment or a concomitant medication. Overdose per se will not be reported as an AE/SAE unless it is an intentional overdose taken with possible suicidal/self-harming intent. Such overdoses should be reported regardless of sequelae.
- The signs, symptoms, and/or clinical sequelae resulting from lack of efficacy will be reported as an AE or SAE if they fulfill the definition of an AE or SAE

Events Meeting the AE Definition

and meet the requirements as per Section 7.5. Also, "lack of efficacy" or "failure of expected pharmacological action" does not constitute an AE or SAE

Events NOT Meeting the AE Definition

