- The investigator is obligated to perform or arrange for the conduct of supplemental measurements and/or evaluations as medically indicated or as requested by the sponsor to elucidate the nature and/or causality of the AE or SAE as fully as possible. This may include additional laboratory tests or investigations, histopathological examinations, or consultation with other healthcare providers.
- New or updated information will be recorded in the originally completed CRF.
- The investigator will submit any updated SAE data to the sponsor within 24 hours of receipt of the information.

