7.1.4. On-treatment Period

On-treatment period is defined as the time from the first dose date of study treatment to the last dose of study drug administration date (when both drugs are permanently discontinued) + 30 days or the earliest date of subsequent anti-cancer drug therapy minus 1 day, whichever occurs first.

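### TEAEs are defined by onset date alone, so a screening-onset AE that worsens on treatment can be left out of the summary tables, and the Amendment 3 change in AE collection can make this uneven over time

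*SAP*

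**What the plan says.** - **TEAE definition (SAP 7.6.4).** "Treatment-emergent adverse events (TEAEs) are defined as AEs with onset date during the on-treatment period". Summary tables show TEAEs only, unless otherwise stated. All other AEs go to listings.
- **Window (SAP 7.1.4).** "On-treatment period is defined as the time from the first dose date of study treatment to the last dose of study drug administration date" plus 30 days, or to the day before subsequent anticancer drug therapy if that is earlier. Worsening from a pre-treatment state is not mentioned.
- **Collection period (Protocol 7.5.1).** From IRB/IEC approval of Amendment 3, active AE collection "begins from the time the patient provides informed consent". The rule before that approval was narrower: "only study procedure related AEs were required to be reported from the time the patient provided informed consent up to the first dose". Screening may last up to 28 days (Protocol 7.1.1).
- **What counts as an AE (Protocol 14.1).** The list of qualifying events includes "Exacerbation of a chronic or intermittent preexisting condition including either an increase in frequency and/or intensity of the condition".
- **Follow-up of a recorded AE (Protocol 14.3).** "New or updated information will be recorded in the originally completed CRF".
- **Missing and partial dates (SAP 7.1.11).** AEs with no start date are taken as treatment-emergent. A partial onset date falling in the month of first dose is moved to the first dose date.

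**The concern.** An AE that exists before dosing and becomes more severe on drug is usually counted as treatment-emergent, because the worsening happened under exposure. The SAP rule looks only at when the record starts. A Grade 1 event with onset on Day -10 that reaches Grade 3 on Day 20, entered as an update to one record, keeps its Day -10 onset. It then appears in no table of TEAEs, Grade 3 or 4 TEAEs, treatment-related TEAEs, or TEAEs leading to dose changes.

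The incidence and severity of AEs is a secondary endpoint. The trial has one arm, so absolute rates are what will be reported and read, and the protocol's rationale rests partly on a different safety profile from an existing combination. The collection rule also changed during the study, so the share of screening events that have a pre-dose record, and can be lost in this way, is not constant over calendar time.

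**Working it through.** No stated figure needs reproducing, because the point concerns a definition. I traced how one clinical course (an event starting between consent and first dose and rising in grade on treatment) is classified under each recording route.

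| Case | AE record and onset date | TEAE under SAP 7.6.4? |
|---|---|---|
| A. After Amendment 3 approval; complete onset date; worsening entered in the existing record | One record, pre-dose onset | No; listing only |
| B. As A, but the site opens a new record for the worsening | Second record, on-treatment onset | Yes |
| C. Before approval; event unrelated to a study procedure | No pre-dose record required, so the exacerbation is normally the first record | Yes |
| D. Procedure-related event, either period | Pre-dose record in both periods, then as A or B | Depends on A or B; no difference by period |
| E. Onset date missing, or partial and in the month of first dose | Generally treated as starting at or after first dose | Yes |

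Three things follow.

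1. A and B are the same event with different results, decided by a recording convention that neither document states. Protocol 14.3 leans towards A and Protocol 14.1 supports B.
2. A and C are the same event with different results, decided by whether it arose before or after IRB/IEC approval of Amendment 3. The TEAE rule is identical for everyone; what changed is which pre-dose events have a record.
3. A against E shows that a vaguely dated screening event is counted while a fully dated one that worsens may not be.

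Next, which worsening is picked up regardless of the TEAE definition:

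- Laboratory parameters: baseline-to-worst shift tables and hepatic criteria (SAP 7.6.5).
- Vital signs, QTcF, LVEF and visual acuity: worst-value or change-from-baseline summaries (SAP 7.6.6 to 7.6.9).
- Dose reductions and interruptions with reasons: taken from the treatment eCRF with no TEAE filter (SAP 7.6.1.1).

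Symptomatic AEs have no such second route. Fatigue, nausea and arthralgia, for example, are among the most common reactions listed in Protocol 2.1.4.

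**Size.** The documents do not give the number of screening-onset AEs, the number that worsened, or the number of participants consented before and after approval. Only the weight of one misclassified participant can be shown, using the planned numbers in Protocol 8.2 as denominators:

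- Treatment-naïve: 1/60 = 1.7 percentage points.
- Previously treated: 1/37 = 2.7 points.
- Total: 1/97 = 1.0 point, or 1/107 = 0.9 point at the expected maximum.

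These apply to a single preferred term. The any-TEAE and Grade 3 or 4 rows change only if that participant has no other qualifying event.

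**The case against.** The strongest reply is that sites may already record such worsening as a new AE. Protocol 14.1 makes an exacerbation an AE at any stage of the study. Protocol 7.3.7 requires worsened, clinically significant ECG findings after first dose to be recorded as AEs. Protocol 14.3 asks for causality on each occurrence. The line about the originally completed CRF is a general follow-up instruction, not a rule on grade increases, and the eCRF and its completion instructions are not among the documents. Safety is also descriptive here, with no comparison or threshold tied to TEAE counts. All of this stands, and it limits the point to a possible misclassification. It does not close the gap, because nothing in either document directs sites to route B.

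Four stronger readings are tempting and are not supported.

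- A reader might infer that a worsening screening AE is never treatment-emergent. Cases B and E show otherwise.
- A reader might infer that only later enrollees are affected. The divide is IRB/IEC approval of Amendment 3, not enrolment; procedure-related AEs were collected before dosing in both periods; and the earlier rule set a minimum without barring other entries.
- A reader might take the approximately 50 patients in the Version 4 change summary as the unaffected group and call the rest about half the study. That text describes them as enrolled under Version 3, the version that corresponds to Amendment 3, so they cannot be assumed to fall under the earlier collection rule.
- A reader might infer that dose changes caused by such events disappear. They remain in the dosing summaries. What may happen is that the tables of TEAEs leading to dose changes do not reconcile with those summaries.

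**Conclusion.** The point holds as a gap in the definition. An onset-only rule, with no stated convention for recording grade increases, can leave on-treatment worsening of a fully dated screening AE out of the TEAE tables. The change in collection at Amendment 3 means that the same course may be counted in one period and not in the other.

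The effect is probably small. It is confined to events that start between consent and first dose, carry a complete date, worsen on treatment, and are updated in place. It falls mainly on symptomatic AEs. The direction is towards under-reporting. There is no between-arm bias, since there is only one arm, and the primary endpoint is untouched. The conclusion assumes that at least some sites update the existing record, which the documents suggest but do not establish. The change is worth making because absolute AE rates are the safety result of this trial and the correction is cheap.

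**What to change.** 1. In SAP 7.6.4, define a TEAE as an AE with onset in the on-treatment period, or with onset before first dose and an increase in CTCAE grade over the pre-treatment grade during that period, dated at the grade increase.
2. State in the CRF instructions whether a grade increase opens a new record or updates the existing one. If it updates the existing record, the grade before dosing and the date of the increase must be obtainable.
3. Query every AE with pre-dose onset that was ongoing at first dose, for all participants, so that the rule applies uniformly. A convention introduced only from now on would add a further break in time, since SAP Version 3.0 already follows the first interim analysis.
4. In the safety reporting, note that pre-dose AE collection widened with IRB/IEC approval of Amendment 3.

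The cost is one SAP sentence, a programming rule, a limited data query, and slightly higher reported TEAE rates. Patients are not affected.

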7.6.5. Clinical Laboratory Evaluations

Required hematology, coagulation, urinalysis and clinical chemistry tests are described in Table 11 of the protocol. Hematology, coagulation, urinalysis and clinical chemistry test results will be presented using the International System of Units (SI units) and, where appropriate, will be graded using NCI CTCAE, Version 4.03.

For laboratory data, baseline is the last available assessment performed prior to the treatment start date/time. If more than one value is available, priority is given to the central assessment versus the local assessment. If more than one central sample is available, priority is given to the assessment marked as *Unscheduled* or *Repeat* assessment. Participants who start treatment and discontinue from the study on the same day may have 2 different sets of data collected on study day 1, one being reported to the cycle 1 day 1 visit, the other reported to the EOT visit. Data reported at the EOT visit are not eligible for baseline selection.

The following laboratory parameters will be summarized by CTCAE grade:

- Hematology: Hemoglobin (anemia/hemoglobin increased), Platelets (platelet count decreased), WBC (white blood cell decreased/increased), Neutrophils (neutrophil count decreased), Lymphocytes (lymphocyte count increased/decreased).
- Chemistry: Albumin (hypoalbuminemia), Alkaline phosphatase (ALP) (alkaline phosphatase increased), Alanine aminotransferase (ALT) (ALT increased), Aspartate aminotransferase (AST) (AST increased), Total bilirubin (TBL) (blood bilirubin increased), Creatinine (creatinine increased), Corrected calcium, CK, Amylase (serum amylase increased), Lipase (lipase increased), Phosphate (hypophosphatemia),

Magnesium (hypomagnesemia/hypermagnesemia), Potassium (hypokalemia/hyperkalemia), Sodium (hyponatremia/hypermnatremia).

- Coagulation: INR (INR increased), PTT or aPTT (Activated partial thromboplastin, time prolonged)

The following laboratory parameters will be summarized by normal range:

- Hematology: Hematocrit, RBC, Monocytes (absolute), Eosinophils (absolute), Basophils (absolute).
- Chemistry: Bicarbonate (CO₂), BUN or urea, Chloride, Glucose, LDH, Total protein, Direct bilirubin.
- Coagulation: Prothrombin Time

The Corrected Calcium will be derived from calcium and albumin results as per the following formula:

$$\text{Corrected Calcium (mmol/L)} = [4 * \text{calcium (mmol/L)} - 0.8 * (0.1 * \text{albumin (g/L)} - 4)] / 4$$

The normal range of Calcium will be used as normal range for Corrected Calcium.

The following summaries will be produced for the hematology and chemistry laboratory data (by laboratory parameter) including central and local laboratory:

- Shift tables using CTCAE grades to compare baseline to the worst post-baseline value for laboratory parameters with CTCAE grades. For the laboratory parameters like blood sodium where participants can be graded for decreased or increased values, the worst post-baseline CTCAE grade will be presented for decrease and increase separately (e.g. hyponatremia and hypernatremia).
- Shift tables using CTCAE grades to compare baseline to the worst post-baseline value for laboratory parameters with CTCAE grades showing participants with Grade ≤ 2 at baseline and worst post baseline Grade 3 or 4.
- Tables reporting the worst post-baseline CTCAE grades for laboratory parameters.
- Shift tables using low, normal, high (as well as low and high combined) classifications to compare baseline to the worst post-baseline value for laboratory parameters where CTCAE grades are not defined.

The following listing will be produced for the laboratory data for all laboratory parameters are defined:

- All laboratory test results will be presented in listings sorted by participant identifier, laboratory test, and date/time of collection with values flagged to show the corresponding CTCAE grades and the classifications relative to the laboratory

reference ranges. Values outside laboratory normal ranges will be flagged where appropriate.

Hepatic Toxicity

Hepatic toxicity will be assessed based on the following Liver Function Tests (LFTs): ALT, AST, ALP, TBL, and INR. Frequency counts and percentages of participants having a newly occurring value in the categories in Table 6 will be provided.

An evaluation of Drug-Induced Serious Hepatotoxicity (eDISH) plot will also be created by graphically displaying

- peak serum ALT(/ULN) vs peak total bilirubin (/ULN) including reference lines at ALT =3×ULN and total bilirubin =2×ULN.
- peak serum AST(/ULN) vs peak total bilirubin (/ULN) including reference lines at AST =3×ULN and total bilirubin =2×ULN.

In addition, a listing of all LFTs values for participants having a newly occurring value in the categories presented in Table 6 will be provided.

Table 6. Hepatic Toxicity Criteria

Parameter	Criterion
ALT	>3xULN; >5xULN; >8xULN;>10xULN;>20 ULN
AST	>3xULN; >5xULN; >8xULN >10xULN;>20 ULN
AT (ALT or AST)	>3xULN; >5xULN; >8xULN >10xULN;>20 ULN
TBL	>1.5xULN, >2xULN
ALP	>2xULN, >3xULN
AT & TBL	AT >3xULN & TBL >2xULN; AT >5xULN & TBL >2xULN; AT >10xULN & TBL >2xULN
ALP & TBL	ALP >3xULN & TBL >2xULN
AT & TBL & ALP	AT >3xULN & TBL >2xULN & ALP <2xULN
AT & TBL & INR	AT >3xULN & (TBL >2xULN or INR >1.5)

